5.7.2. Analysis of Secondary Efficacy Endpoints

No secondary efficacy variables are collected for this study

5.7.3. Analysis of Other Exploratory Endpoints

The following exploratory endpoints will be summarized descriptively:

1. Cumulative incidence of symptomatic (broad term), RT-PCR-confirmed SARS-CoV-2 infection cases during the follow-up period
2. Cumulative incidence of RT-PCR-confirmed SARS-CoV-2 infection cases (regardless of symptoms) during the EAP
3. Proportion of participants with COVID-19-related hospitalization, emergency room visit, urgent care center visit or death during the EAP and follow-up period
4. Maximum SARS-CoV-2 RT-qPCR viral load (log₁₀ copies/mL) in NP swab samples among individuals with ≥ 1 RT-qPCR positive test that has an onset during the EAP

5. Viral variant characteristics of SARS-CoV-2 in participants who become infected post-baseline

5.7.4. Adjustment for Multiple Comparison

Due to study early terminations, no multiple adjustments will be performed for any analyses.

5.8. Analysis of Safety Data

Secondary safety endpoints are

1. Proportion of participants with grade ≥ 3 treatment-emergent adverse events (TEAEs), during the EAP and follow-up period
2. Proportion of participants with TEAEs leading to study drug discontinuation, during the EAP and follow-up period
3. Proportion of participants with treatment-emergent serious adverse events (SAEs) during the EAP and follow-up period
4. Proportion of participants with adverse events of special interest (AESIs) during the EAP

For safety variables, the following observation periods are defined:

- The pretreatment period is defined as the time from the signing of the ICF to before study drug administration.
- The EAP is defined as the day from first dose of study drug to day 169 ± 7 days
- The Follow-up period is defined as the end of the EAP to the end of the Follow-up Period (ie, the last study visit).

The safety analysis will be based on the reported AEs and other safety information (clinical laboratory evaluations, and vital signs). The summary of AE results will be presented for each treatment group for each of three TEAE periods: treatment-emergent EAP (TEEAP), treatment-emergent follow-up period (TEFUP), and overall study period (i.e., combined across the TEEAP and TEFUP). For laboratory and vital sign results they will be presented for each treatment group for each of three periods: EAP, follow-up, and overall study period.

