### **11.3.2. Safety Analysis Set**

The safety analysis set (SAF) includes all participants who received any study drug; it is based on the treatment received (as treated). Determination of “as treated” will be based on the actual study drug received, with details provided in the SAP. Treatment compliance/administration and all clinical safety variables will be analyzed using the SAF.

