3.2. Safety Analysis Set

The safety analysis set (SAF) includes all participants who received any study drug; it is based on the treatment received (as treated). Determination of “as treated” will be based on the actual study drug received. Treatment compliance/administration and all clinical safety variables will be analyzed using the SAF.

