4.5. Efficacy Variable

4.5.1. Primary Efficacy Variable

Primary efficacy variable is cumulative incidence of symptomatic (broad term), RT-PCR-confirmed SARS-CoV-2 infection cases during the efficacy assessment period (EAP). The conditions for symptomatic SARS-CoV-2 infection are as follows:

- At least 1 sign or symptom (broad term definition) confirmed by a study clinician (investigator or designee) to be related to COVID-19, **and**
- A positive SARS-CoV-2 RT-PCR result (local or central analysis), **with**
- The sign/symptom onset date and the date of collection for the positive sample occurring within ± 7 days of one another

The primary endpoint will analyze symptomatic SARS-CoV-2 infection during the efficacy assessment period (EAP). The EAP is defined as the day 2 to day 169 +7 days . In addition, following rules will be applied to the primary analyses:

- Time to first symptomatic infection is defined as the first date of having either central or local lab determined positive test result.
- Subjects do not experience any symptomatic infection will be censored at last observed time point.
- Subjects who die at any time in the study or discontinue the study earlier (did not get any infections) will be censored at the end of study in case of final database lock.
- Subjects with COVID-19 symptoms that are missing a central lab determined RT-qPCR test during the EAP but have a positive SARS-CoV-2 test from a local lab will be considered as having a symptomatic infection if any of the symptoms occurred within 7 days of the positive SARS-CoV-2 test that was observed during the EAP.
- If subjects took optional dose of 1200mg, all the data after the dose will be removed from the efficacy analyses.

If subjects took investigational, authorized, or approved COVID-19 vaccines within 90 days of the last dose of study drug (or per current CDC recommendations) (CDC, 2021) or any covid-19 treatment medications for prevention after starting study treatment (Anti SARS-CoV-2 antibodies including Bamlanivimab/ Etesevimab, Casirivimab/ Imdevimab (REGEN-COV), Sotrovimab or Tixagevimab/ Cilgavimab (Evusheld); remdesivir; Nirmatrelvir/ Ritonavir (Paxlovid); Molnupiravir, all the efficacy data after these treatment will be removed from efficacy analyses.

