5.6.2. Exposure to Investigational Product

The duration of study treatment exposure will be defined as day 1 through 4 weeks, ie, 28 days, after the last dose for a participant in the Q4W arms and day 1 through 12 weeks, ie, 84 days after the last dose for a participant in the Q12W arm. The duration of the study will be through the follow-up period defined as end of EAP through day 253 (± 14 days). Treatment exposure and study duration will be evaluated in the SAF.

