5.8.1. Adverse Events

All AEs reported in this study will be reported by the preferred term (PT), and the primary system organ class (SOC). The number and percentage of subjects with TEAEs will be summarized by treatment group.

Summaries will include:

- Overview of TEAEs, i.e., overall number (%) of subjects with any TEAE, Serious TEAE, TEAE leading to death, TEAE leading to study withdrawn

- Overview of non-COVID TEAEs (not related to the patients's underlying disease and/or not related to treatments for the underlying conditions), i.e., overall number (%) of subjects with any TEAE, Serious TEAE, TEAE leading to death, or TEAE leading to study withdrawn
- Overview of AESI, i.e., overall number (%) of subjects with any AESI, grade 3 or greater injection site reactions, grade 2 or greater hypersensitivity reactions, AESI leading to death, or AESI leading to study drug withdrawn)
- TEAEs by primary SOC and PT
- TEAEs by severity (according to the grading scale appendix Section 10.3), presented by primary SOC and PT
- TEAEs by relationship to treatment (related, not related), presented by primary SOC and PT
- Treatment-emergent SAEs by primary SOC and PT
- Treatment-emergent AESIs by primary SOC and PT
- TEAEs leading to study withdrawn by primary SOC and PT
- Treatment-emergent AESIs leading to study withdrawn by primary SOC and PT
- Treatment-emergent AESIs by severity, presented by primary SOC and PT
- Number of subjects who died during TEEAP, TEFUP, and the study period, respectively, and reason for death
- TEAEs leading to death
- AESIs leading to death by SOC and PT.

In addition, the number (%) of subjects symptoms assessment collected in the COVID-19 symptoms assessment eCRF will be summarized by treatment group. The descriptive statistics of the duration (days) of each COVID-19 symptom will also be presented. Subject listing of COVID-19 symptoms including the details such as the start date, end date, and duration of each symptom will be provided. In addition, subject listing of SAEs, AESI, TEAEs related to study drug, and TEAEs leading to study drug withdrawn will also be presented.

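### Safety summaries are not cut at the optional 1200 mg active dose, and the SAP gives no as-treated rule for participants who take it

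*SAP*

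**What the plan says.** **Optional dose.** The Amendment 2 procedures in the protocol, repeated in SAP 1.1, offer a single 1200 mg subcutaneous active dose about four weeks after the most recent dose, whatever the randomised arm. Only participants who already had casirivimab+imdevimab as post-infection treatment are barred from it.

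**Efficacy.** SAP 4.5.1 has an explicit rule: "If subjects took optional dose of 1200mg, all the data after the dose will be removed from the efficacy analyses".

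**Safety.** SAP 5.8 says of adverse events: "The summary of AE results will be presented for each treatment group for each of three TEAE periods". It continues: "For laboratory and vital sign results they will be presented for each treatment group for each of three periods". SAP 5.8.1 adds: "The number and percentage of subjects with TEAEs will be summarized by treatment group". One of its tables is "TEAEs by relationship to treatment (related, not related), presented by primary SOC and PT". SAP 4.6.1, 5.8, 5.8.1 and 5.8.3 do not mention the optional dose.

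**As-treated rule.** Protocol 11.3.2 says the determination is "based on the actual study drug received, with details provided in the SAP". SAP 3.2 says it "will be based on the actual study drug received" and adds no details.

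**Exposure.** SAP 5.6.2 counts exposure to 28 days after the last dose in the Q4W arms, and from "day 1 through 12 weeks, ie, 84 days after the last dose for a participant in the Q12W arm". It does not say whether the optional dose is a last dose for this purpose.

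**The concern.** A placebo participant who takes the optional dose has had placebo and then active drug. The as-treated sentence allows two readings. The participant may stay in the placebo column, so that events after 1200 mg of active drug count as placebo events. Or the participant may move to an active column, so that placebo time counts as active and no column matches the regimen received. Two programmers could build different tables from the same SAP. Takers in the two 300 mg arms raise the same question. In arm 1, which had 1200 mg on day 1 (protocol 8.1), the mixing is mildest.

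Safety is the output the plan still commits to: safety endpoints will be summarised, while selected efficacy, PK and immunogenicity data only may be. Collection was also widened beyond grade 3 and above, so mild reactions now reach the all-grade and relationship-to-treatment tables. Those tables are the most exposed to a wrong column label.

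**Working it through.** **1. Group size.** SAP 2.1 gives 66 randomised and about 16 to 17 per group. Under the 1:1:1:1 allocation in protocol 8.1, 66/4 = 16.5, which agrees. One misplaced participant moves a column by about 1/16.5 = 6 points.

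**2. Timing.** Inputs: dosing every 28 days from day 1; optional dose 28 days after the most recent dose and final call 85 days after the last dose (protocol Table 2); safety efficacy assessment period (EAP) to day 169 ± 7, so at most day 176 (SAP 5.8). After k assigned doses, the optional dose is on day 1 + 28k and the call 85 days later.

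The documents give neither k nor uptake u, so both are varied.
- Taker's share of follow-up after the optional dose: 85/(28k + 85).
- Arm-level share: 85u/[u(28k + 85) + (1 − u)(28(k − 1) + 85)].

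| k | Optional dose, day | Final call, day | Taker share (= arm share at u = 100%) | Arm share, u = 25% | Arm share, u = 50% |
|---|---|---|---|---|---|
| 1 | 29 | 114 | 75% | 23% | 43% |
| 2 | 57 | 142 | 60% | 18% | 33% |
| 3 | 85 | 170 | 50% | 14% | 27% |
| 4 | 113 | 198 | 43% | 12% | 23% |
| 5 | 141 | 226 | 38% | 10% | 20% |
| 6 | 169 | 254 | 34% | 9% | 18% |

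Every nominal optional-dose day is inside the EAP. Only with the windows at their limits does it pass the edge: 141 + 7 + 28 + 7 = day 183. For k = 1 to 3, all 85 days after the dose also fall inside the EAP. The existing period split therefore does not separate assigned from optional exposure.

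**3. Events under the wrong label.** Protocol 3.3.1 gives any-grade injection-site reaction rates of 4% (active) and 2% (placebo) after a single 1200 mg dose in another trial.
- Chance that at least one reaction after the active dose is counted under placebo, 1 − 0.96^n: n = 8 gives 28%; n = 17 gives 50%.
- Same chance for the 2-point excess over placebo, 1 − 0.98^n: n = 8 gives 15%; n = 17 gives 29%.
- Expected placebo-column rate, 1 − (1 − 0.02)(1 − 0.04u), against 2% without the optional dose: 3.0% at u = 25%, 4.0% at 50%, 5.9% at 100%.

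**4. Effect on the between-arm gap.** Six monthly 1200 mg doses in adult volunteers gave 34.6% against 15.8% (protocol 3.3.1), a gap of 18.8 points. If both arms gain an independent extra risk 0.04u, the gap becomes 18.8 × (1 − 0.04u).
- u = 50%: 18.42, a fall of 0.38 points.
- u = 100%: 18.05, a fall of 0.75 points.
- Standard error at 16.5 per arm: √[(0.346 × 0.654 + 0.158 × 0.842)/16.5] = 14.8 points.
- Extreme unequal case, all placebo and no active participants taking the dose: (1 − 0.158) × 0.04 = 3.4 points.

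**5. Exposure, if the last dose includes the optional one.** After one assigned dose, a taker in a Q4W arm (placebo is dosed Q4W) shows 28 + 28 = 56 days. A taker in the Q12W arm shows 28 + 84 = 112 days. The same 1200 mg dose counts as 28 days in one arm and 84 in the other.

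**The case against.** The strongest reply is that little depends on this. SAP 1 says no hypothesis is evaluable, and all analyses are descriptive. With equal uptake the gap hardly moves (step 4). Three of the four arms had already received the drug, so clear placebo-versus-active mislabelling concerns one arm. SAP 5.8.1 provides listings of serious events, events of special interest (AESIs), related events and events leading to drug withdrawal, and the optional dose is recorded. In groups of 16 or 17, a reader could place each listed event before or after the dose. AESIs are probably little affected: injection-site reactions qualify only at grade 3 or above, and the nearest hypersensitivity figure in protocol 3.3.1 is at most 0.3% for grade 2 or higher infusion-related reactions, though by the intravenous route.

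Most of this stands, and it limits the importance. It does not remove the problem. Listings support case review but do not correct by-arm percentages, and they leave out events that are neither serious, related, of special interest nor a cause of withdrawal. The missing as-treated rule also remains.

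On exposure, a reader might infer from footnote 1 in protocol 9.1.2 that SAP 5.6.2 does count the optional dose. That footnote sets only the timing of the final call, and 5.6.2 carries over protocol wording written for the assigned regimens. The text is ambiguous and does not establish that exposure will be miscounted.

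**Conclusion.** The point holds and should be fixed, with modest importance. Followed as written, the SAP can count events after active drug under placebo, the clearest case, or under a 300 mg arm, and it leaves the as-treated label of takers undefined.

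The size depends on two quantities the documents do not give. Over one to six assigned doses, the arm-level share of follow-up after the optional dose is 9–23%, 18–43% and 34–75% at assumed uptakes of 25%, 50% and 100%. The chance of at least one injection-site reaction after active drug appearing under placebo is 28% to 50% for 8 to 17 takers, or about 15% to 29% for the drug-attributable excess. These figures borrow any-grade rates from another trial and assume nominal visit timing.

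Two stronger conclusions might be inferred, and the documents support neither. One is that the between-arm safety comparison is materially biased: at the 4% rate and equal uptake the gap shifts by less than one point against a standard error of 14.8, and no formal inference is planned. The other is that most follow-up is contaminated: that needs few assigned doses together with high uptake, and the documents establish neither.

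**What to change.** - **SAP 3.2:** state that the as-treated label is based on study drug received before any optional dose or post-infection casirivimab+imdevimab. The second clause is needed because post-infection recipients cannot take the optional dose, so a cut at that dose alone would never separate them.
- **SAP 5.8, 5.8.1 and 5.8.3:** keep the planned EAP, follow-up and overall tables, so the windows of the secondary safety endpoints do not change. Add the key AE, AESI, related-TEAE and vital-sign summaries by that label up to the first non-assigned active dose, and a separate summary or listing after it by original arm. At the dose visit, the pre-dose vital signs belong before the cut and the reading at 60 minutes or later belongs after it.
- **Denominators:** give number at risk and person-time on each side of the cut. Follow-up before the optional dose is unequal: after one assigned dose, a taker contributes 28 days and a non-taker 85.
- **SAP 5.6.2:** report assigned-treatment exposure, ending at the optional dose, separately from optional-dose exposure.

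The cost is some SAP text and one small table set for 66 participants, using a dose date already recorded. No dosing or treatment rule changes. The downside is shorter follow-up in the pre-dose tables. At an assumed 50% uptake after one assigned dose, 16.5 × (0.5 × 28 + 0.5 × 85) = 932 person-days per arm stay before the cut and 16.5 × 0.5 × 85 = 701 move after it. Nothing is lost from the planned overall tables.

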5.8.1. Adverse Events

All AEs reported in this study will be reported by the preferred term (PT), and the primary system organ class (SOC). The number and percentage of subjects with TEAEs will be summarized by treatment group.

Summaries will include:

- Overview of TEAEs, i.e., overall number (%) of subjects with any TEAE, Serious TEAE, TEAE leading to death, TEAE leading to study withdrawn

- Overview of non-COVID TEAEs (not related to the patients's underlying disease and/or not related to treatments for the underlying conditions), i.e., overall number (%) of subjects with any TEAE, Serious TEAE, TEAE leading to death, or TEAE leading to study withdrawn
- Overview of AESI, i.e., overall number (%) of subjects with any AESI, grade 3 or greater injection site reactions, grade 2 or greater hypersensitivity reactions, AESI leading to death, or AESI leading to study drug withdrawn)
- TEAEs by primary SOC and PT
- TEAEs by severity (according to the grading scale appendix Section 10.3), presented by primary SOC and PT
- TEAEs by relationship to treatment (related, not related), presented by primary SOC and PT
- Treatment-emergent SAEs by primary SOC and PT
- Treatment-emergent AESIs by primary SOC and PT
- TEAEs leading to study withdrawn by primary SOC and PT
- Treatment-emergent AESIs leading to study withdrawn by primary SOC and PT
- Treatment-emergent AESIs by severity, presented by primary SOC and PT
- Number of subjects who died during TEEAP, TEFUP, and the study period, respectively, and reason for death
- TEAEs leading to death
- AESIs leading to death by SOC and PT.

In addition, the number (%) of subjects symptoms assessment collected in the COVID-19 symptoms assessment eCRF will be summarized by treatment group. The descriptive statistics of the duration (days) of each COVID-19 symptom will also be presented. Subject listing of COVID-19 symptoms including the details such as the start date, end date, and duration of each symptom will be provided. In addition, subject listing of SAEs, AESI, TEAEs related to study drug, and TEAEs leading to study drug withdrawn will also be presented.

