#### 8.3.2. Study Drug Discontinuation

Participants who permanently discontinue from study drug should be encouraged to remain in the study. Participants who permanently discontinue from study drug and who opt to withdraw from the study will be asked to complete study assessments, per Section 9.1.1.

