##### 8.3.2.1. Reasons for Permanent Discontinuation of Study Drug

Study drug dosing will be permanently stopped in the event of:

- Grade  $\geq 3$  injection-site reaction or grade  $\geq 3$  hypersensitivity reaction determined to be related to study drug

- Serious adverse event or other potentially life-threatening (grade 4) event that is determined to be related to study drug
- Investigator's clinical judgment, in coordination with principal investigator, that it is in the best interest of the participant
- Receipt of a COVID-19 vaccine during the study
- A positive baseline (day 1) result for SARS-CoV-2 from central laboratory RT-qPCR (however, eligible for additional treatment as defined in Section [6.4.7](#))
- Receipt of post-infection treatment with casirivimab+imdevimab (Section [6.4.4](#))
- Participant withdrawal of consent
- Unblinding of participant

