5.5. Subject Disposition

Subject study status will be summarized by treatment group and overall for the study.

The following will be provided:

- Number of screened subjects, defined as signed the ICF
- Number of randomized subjects
- Number of subjects randomized but who did not receive study treatment

- Number of subjects who discontinued the study, and the reasons for discontinuation
- A listing of subjects treated but not randomized, subjects randomized but not treated, and subjects randomized but not treated as randomized
- A listing of subjects prematurely discontinued from the study, along with reasons for Discontinuation
- A summary of analysis sets including randomized subjects and randomized subjects by treatment groups, ITT, mITT, SAF, PK, immunogenicity (AAS).

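### SAP 5.8.1 specifies its TEAE summary tables by withdrawal from the study, while the secondary safety endpoint is TEAEs leading to discontinuation of study drug

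*SAP*

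**What the plan says.** SAP 5.8 lists four secondary safety endpoints. The second is "Proportion of participants with TEAEs leading to study drug discontinuation, during the EAP and follow-up period", which matches protocol 4.2.

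SAP 5.8.1 then lists the summaries. The overview of all TEAEs ends with "TEAE leading to death, TEAE leading to study withdrawn", and the non-COVID TEAE overview uses the same term. The breakdown table is "TEAEs leading to study withdrawn by primary SOC and PT". The AESI overview instead has "AESI leading to death, or AESI leading to study drug withdrawn", while the matching AESI table by SOC and PT goes back to withdrawal from the study. At the end of the section, among the subject listings, "TEAEs leading to study drug withdrawn will also be presented".

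For disposition, SAP 5.5 plans "Number of subjects who discontinued the study, and the reasons for discontinuation". It has no corresponding line for discontinuing study treatment, although protocol 11.4.1 has one, with reasons.

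On the difference between the two events, protocol 8.3.2 says: "Participants who permanently discontinue from study drug should be encouraged to remain in the study".

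**The concern.** Stopping the drug and leaving the study are separate events, and the protocol is written to keep them apart. A participant who stops dosing because of an adverse event and stays in follow-up, as the protocol asks, meets the endpoint but does not belong in a row for study withdrawal. A programmer who builds the tables in SAP 5.8.1 as written will therefore count something other than the endpoint. No other listed summary gives the endpoint's number and percentage by arm.

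Safety is the main remaining output. With 66 participants enrolled, SAP section 1 states that none of the hypotheses can be evaluated, and SAP 1.1 promises that all safety endpoints will be summarized. The proportion stopping drug because of adverse events is a basic tolerability measure, and tolerability of repeated injections is a secondary objective.

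**Working it through.** No sample-size or power figure bears on this point. The check compares the endpoint with each planned output.

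1. **Endpoint** (protocol 4.2; SAP 5.8, item 2). Event: a TEAE leading to a stop of study drug. Measure: proportion of participants. Window: EAP and follow-up.

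2. **Planned outputs** (SAP 5.8.1).
   - Overview of all TEAEs: leaving the study.
   - Overview of non-COVID TEAEs: leaving the study.
   - TEAE table by SOC and PT: leaving the study.
   - AESI overview: stopping drug, AESIs only.
   - AESI table by SOC and PT: leaving the study.
   - Subject listing: stopping drug, all TEAEs, but participant by participant rather than as a number and percentage by arm.

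   The other three secondary safety endpoints each have a related summary: TEAEs by severity, treatment-emergent SAEs, and AESIs. This one does not.

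3. **Are the events different?** Yes. Besides 8.3.2, protocol 8.3.2.1 lists adverse-event reasons for permanently stopping drug, among them "Serious adverse event or other potentially life-threatening (grade 4) event that is determined to be related to study drug". These rules end dosing. They do not end study participation.

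4. **Where the wording comes from.** In protocol 11.4.5.1, the overview row refers to discontinuing the study, and the SOC/PT table refers to discontinuation without saying of what. The same section's list of targeted TEAEs also uses the unqualified term and cites protocol 10.1, where it means study drug. The ambiguity therefore starts in the protocol, and the SAP resolves the SOC/PT table towards the study. SAP 1.2.4 declares one change from the protocol, that some exploratory efficacy endpoints will not be reported. It declares no safety change.

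5. **Scale.** Let n be the arm size, d the number who stop drug for a TEAE but stay in the study, and w the number who leave the study for a TEAE without a drug stop. Using the withdrawal proportion as the endpoint gives an error of (w − d)/n.
   - SAP 2.1 gives 66 participants, about 16 to 17 per arm (66/4 = 16.5).
   - For d = 1 and w = 0, the error is −1/17 = −5.9 percentage points to −1/16 = −6.3 percentage points.
   - The documents give neither d nor w, so the actual error cannot be computed.

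**The case against.** A reader might infer that the endpoint has been dropped. The documents do not support that. SAP 5.8 names it as a proportion and says AE results will be presented by treatment group for the EAP, follow-up and overall periods. The list in 5.8.1 is introduced as what the summaries will include, so it need not be complete. The data are still collected (protocol Table 2), and with 66 participants the count can be recovered from the planned listing. All of this stands. What is missing is an explicit table, and the tables that are explicit name the other event.

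A reader might also infer that the reported rate will be understated, or will be zero whatever the true rate. That follows only if the withdrawal count is presented as the endpoint, and no section says it will be. A row labelled study withdrawal that counts study withdrawals is correct for what it is. Zero would further require that nobody left the study because of a TEAE. Nor is one set strictly contained in the other: a TEAE after the last dose could lead someone to leave the study with no drug left to stop.

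The wording may simply be loose. The AESI overview and its SOC/PT table, which would normally describe the same events, use different terms, and so do the TEAE tables and the TEAE listing. The documents do not settle what was meant. That weakens any claim of a deliberate change, but it is also a reason to correct the text.

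On disposition, protocol 11.6 allows a prematurely terminated study to summarize only the parameters needed for the development program or for regulatory reporting. Sponsor closure may also account for most treatment discontinuations. Both points are fair. A count with reasons would let adverse-event stops be told apart from closure, but it would not itself deliver the TEAE endpoint.

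**Conclusion.** The mismatch is real and modest. As written, the TEAE overviews and the SOC/PT table in SAP 5.8.1 count TEAEs leading to study withdrawal, while the endpoint is TEAEs leading to study drug discontinuation. For all TEAEs, the latter is planned only as a listing. Substituting one count for the other would probably understate the endpoint, because the protocol encourages people who stop drug to remain. Each net missed participant would cost 5.9 to 6.3 percentage points in an arm.

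That scale assumes denominators of 16 to 17 treated participants. If some randomized participants were never dosed, the safety set is smaller and each participant weighs slightly more. The direction assumes d exceeds w, which is likely but not certain.

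The consequence is bounded: SAP section 1 redesignates all primary and secondary endpoints as exploratory, the analyses are descriptive, and the count remains recoverable.

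**What to change.** In SAP 5.8.1:

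- Add to both TEAE overviews a row giving the number and percentage by arm with TEAEs leading to study drug discontinuation.
- Add a table of the same events by SOC and PT. Present the rows and the table for the EAP, follow-up and overall periods.
- Keep study withdrawal as its own row. The protocol's overview lists it, so the change is an addition and not a replacement.
- Use the two terms consistently throughout, including in the AESI overview, the AESI table by SOC and PT, and the listings.

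In SAP 5.5, restore the count of participants who discontinued study treatment, with reasons, as listed in protocol 11.4.1.

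The cost is SAP wording and a small change to the table shells. No new data are needed for the endpoint, since the close-out schedule in protocol Table 2 already collects TEAEs leading to study drug discontinuation.
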